7.1.1.3. Analyses on Primary Efficacy Endpoint by Subgroups

The primary endpoint, HbA_{1c} change from Baseline at Week 26, will also be examined by the subgroups of a number of variables, such as baseline HbA_{1c} category, gender, race, ethnicity, age category, baseline BMI category, region, duration of diabetes category and current use of metformin (see Appendix 9), using a MMRM model that is similar to the model for the primary analysis but also includes the subgroup-variable-by-treatment-by-visit week interaction term (as well as subgroup-variable-by-treatment and subgroup-variable-by-visit week). The adjusted mean difference and confidence interval for each level of the subgroup will be estimated from the MMRM model and the p-values for the treatment by subgroup interactions will be reported.

7.1.1.4. Sensitivity Analysis

Sensitivity analyses will be performed for the primary efficacy endpoint to assess the robustness of the primary efficacy analysis results with respect to departures from the assumption that missing primary endpoint data are missing at random. Detailed methodology is provided in Appendix 6.

7.1.2. Planned Efficacy Statistical Analyses

Primary Statistical Analyses
Endpoint(s)

 Change from Baseline in HbA_{1c} at Week 26
Model Specification

 Change from Baseline in HbA_{1c} = Baseline HbA_{1c} + Treatment + Region + Age Category + Current Use of Metformin + Visit Week + Treatment-by-Visit Interaction + Baseline HbA_{1c}-by-Visit Week Interaction (Model 1)
Model Checking & Diagnostics

 Refer to Appendix 11: Model Checking and Diagnostics for Statistical Analyses
Model Results Presentation

 The least squares mean of the treatment difference at Week 26 estimated from the MMRM model and its 1-sided 97.5% confidence interval Descriptive statistics for the observed HbA_{1c} and change from Baseline HbA_{1c} Plot of the least squares means (and standard errors) of change from Baseline HbA_{1c} by treatment group Refer to Appendix 14: List of Data Displays
Supportive Statistical Analysis

 The generalizability of the treatment effect will be evaluated within a supportive MMRM model that adds terms for treatment-by-variable interaction. The variables include baseline HbA_{1c}, region, age category, and current use of metformin. The primary endpoint will also be analyzed using Model 1 above in the Per-Protocol Population
Model Specification

 Change from Baseline in HbA_{1c} = Baseline HbA_{1c} + Treatment + Region + Age Category + Current Use of Metformin + Visit Week + Treatment-by-Visit Interaction + Baseline HbA_{1c}-by-Visit Week Interaction + Treatment-by-Variable + Visit Week-by-Variable + Treatment-by-Visit Week-by-Variable. Refer to Appendix 11: Model Checking and Diagnostics for Statistical Analyses for SAS code
By-Subgroup Statistical Analysis

 The subgroup analyses will be performed using MMRM models. The subgroups include baseline HbA_{1c} category, gender, race, ethnicity, age category, baseline BMI category, region, duration of diabetes category and current use of metformin. Refer to Appendix 9: Examination of Covariates, Subgroups & Other Strata.
Model Specification

 Change from Baseline in HbA_{1c} = Baseline HbA_{1c} + Treatment + Region + Age Category + Current Use of Metformin + Visit Week + Treatment-by-Visit Interaction + Baseline HbA_{1c}-by-Visit Week Interaction+ Treatment-by-Visit Week-by-Variable + Treatment-by-Variable + Visit Week-by-Variable. Refer to Appendix 11: Model Checking and Diagnostics for Statistical Analyses for SAS code
Sensitivity Statistical Analysis with Respect to Missing Data MAR Assumption

 Refer to Appendix 6, Section 11.6.3: Sensitivity Analysis on the Primary Efficacy Endpoint

8. SECONDARY AND EXPLORATORY STATISTICAL ANALYSES

8.1. Secondary Efficacy Analyses

8.1.1. Overview of Planned Secondary Efficacy Analyses

The secondary efficacy analyses will be based on the Full Analysis (FA) population, unless otherwise specified.

Table 4 provides an overview of the planned secondary efficacy analyses, with full details of data displays being presented in [Appendix 14: List of Data Displays](#).

Table 4 Overview of Planned Secondary Efficacy Analyses

	Stats Analysis			Summary		Individual	
	T	F	L	T	F	F	L
Key Secondary Endpoints							
Proportion of subjects treated with once-weekly albiglutide that are able to discontinue insulin lispro at Week 4 and do not meet prespecified criteria for severe, persistent hyperglycemia through Week 26	Y			Y			Y
Percentage of subjects with severe or documented symptomatic hypoglycemia through Week 26	Y			Y			Y
Change from Baseline in body weight at Week 26 and over time	Y	Y		Y	Y		Y
Prescribed total daily insulin dose at Week 26	Y	Y		Y	Y		Y
Supportive Secondary Endpoints							
HbA _{1c} change from Baseline over time	Y	Y		Y	Y		
FPG change from Baseline at Week 26 and over time	Y	Y		Y	Y		Y
Proportion of subjects achieving a HbA _{1c} <7.0% at Week 26 and over time	Y			Y			
Proportion of subjects achieving a HbA _{1c} <6.5% at Week 26 and over time	Y			Y			
Incidence and time to meeting prespecified criteria for severe, persistent hyperglycemia at Week 26	Y	Y		Y			Y
Prescribed total daily insulin dose (total units and total units/kg body weight) at the Baseline/Randomization and Week 4, 10, and 18 visits	Y	Y		Y	Y		
Prescribed total daily basal insulin (insulin glargine) (total units and total units/kg body weight) at the Baseline/Randomization and Week 4, 10, 18, and 26 visits	Y	Y		Y	Y		

	Stats Analysis			Summary		Individual	
	T	F	L	T	F	F	L
Prescribed total daily basal insulin (insulin glargine) (total units and total units/kg body weight) at the Baseline/Randomization and Week 4, 10, 18, and 26 visits	Y	Y		Y	Y		
Prescribed total daily bolus insulin (insulin lispro) (total units and total units/kg body weight) at the Baseline/Randomization and Week 4, 10, 18, and 26 visits	Y	Y		Y	Y		
Total number of weekly insulin injections (7 days) to achieve glycemic control at Baseline/Randomization and Week 4, 10, 18, and 26	Y	Y		Y	Y		
Composite endpoints (after 26 weeks of treatment): Percentage of subjects achieving HbA _{1c} <7.0% without weight gain	Y			Y			
Composite endpoints (after 26 weeks of treatment): Percentage of subjects achieving HbA _{1c} <7.0% without severe or documented symptomatic hypoglycemia	Y			Y			
Composite endpoints (after 26 weeks of treatment): Percentage of subjects achieving HbA _{1c} <7.0% without weight gain and without severe or documented hypoglycemia	Y			Y			

NOTES :

- T = Table, F = Figure, L = Listing, Y = Yes display generated.
- Stats Analysis = Represents TFL related to any formal statistical analyses (i.e. modelling) conducted.
- Summary = Represents TFL related to any summaries (i.e. descriptive statistics) of the observed raw data.
- Individual = Represents FL related to any displays of individual subject observed raw data.

Following review of the data, additional analyses maybe conducted to further support the evaluation and interpretation of the data.

8.1.2. Key Secondary Efficacy Endpoints

8.1.2.1. Proportion of Subjects Who Do Not Meet Prespecified Criteria for Severe, Persistent Hyperglycemia through Week 26

For this key secondary endpoint, subjects who do not meet prespecified criteria for severe, persistent hyperglycemia through Week 26 will be defined operationally as those subjects treated with once-weekly albiglutide that are able to replace prandial insulin without lispro re-introduction through Week 26. Note: For lispro re-introduction through Week 26 the time window is defined up to Week 25.

Proportion of subjects that are able to discontinue insulin lispro at Week 4 and do not meet prespecified criteria for severe, persistent hyperglycemia through Week 26 will be summarized descriptively for all the Albiglutide + Insulin Glargine arm subjects and for

subgroups of baseline HbA_{1c} category (<8.0%, ≥8.0%), region, (<65 years versus ≥65 years), current use of metformin (Yes, No) in the FA population. The 95% confidence interval of the proportions of subjects will be provided.

The insulin lispro that was re-introduced to albiglutide subjects will be characterized. Summary statistics for the number of injections, total dose, and time-to-re-introduction will be presented.

Additional exploratory analyses to identify potential risk factors for lispro re-introduction will be investigated. Potential risk factors include: baseline HbA_{1c}, baseline HbA_{1c} category, age, age category, metformin-use, duration of diabetes, weight, BMI, BMI category, time in insulin (at baseline), baseline HbA_{1c}, and total insulin dose at baseline. Time in insulin (at baseline) is defined as the earliest start date of prior insulin medications taken minus the date of first date of randomized study medication, plus 1.

8.1.2.2. Percentages of Subjects with Severe or Documented Symptomatic Hypoglycemia through Week 26

The percentage of subjects with severe or documented symptomatic hypoglycemia will be summarized descriptively by treatment and analyzed using a Cochran-Mantel-Haenszel (CMH) test, stratified by baseline HbA_{1c} category, region, age category (<65 years versus ≥65 years), current use of metformin (Yes, No) in the FA population.

As supportive analysis, logistic regression models adjusting for baseline HbA_{1c} category, region, age category and current use of metformin will be used to quantify the treatment effects. Odds ratio for treatment and the associated confidence interval will be used to estimate the treatment difference.

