5.1.2. Dosing Guidance During the Treatment Period

The dosing guidance for albiglutide, insulin lispro, insulin glargine, and metformin from Baseline/Randomization through the end of the Treatment Period is summarized in **Table 2**.

Table 2 Dosing Guidance for Albiglutide, Insulin Lispro, Insulin Glargine, and Metformin Treatment

Medication	Albiglutide + Insulin Glargine Group	Insulin Glargine + Insulin Lispro Group
Albiglutide	Baseline/Randomization: Start weekly SC injection at 30 mg. Week 4: Uptitrate to 50 mg weekly SC injection for the remainder of the Treatment Period.	None
Insulin lispro	Baseline/Randomization: Each insulin lispro dose will be downtitrated to half that used in the Standardization Period. ¹ Week 4: Stop insulin lispro for the remainder of the Treatment Period; insulin lispro may be re-introduced after Week 8 (See Section 5.1.3.5)	Baseline/Randomization: Continue at the same doses as at the end of the Standardization Period and adjust doses as per instructions in Section 5.1.3.2.
Insulin glargine	Continue at the same dose as at the end of the Standardization Period ¹ and adjust dose as per instructions in Section 5.1.3.2.	Continue at the same dose as at the end of the Standardization Period and adjust dose as per instructions in Section 5.1.3.2.

Medication	Albiglutide + Insulin Glargine Group	Insulin Glargine + Insulin Lispro Group
Metformin	Subjects will remain on their current dose for the duration of their participation in the study. ²	Subjects will remain on their current dose for the duration of their participation in the study. ²
Re-introduction of insulin lispro (if required)	After Week 8: See Section 5.1.3.5	Not applicable

SC = subcutaneous.

1. As described in Section 1.3.1, the risk of hypoglycemia is increased when albiglutide is used in combination with insulin; therefore, subjects may require a lower dose of insulin and should be monitored closely.
2. Unless a decline in kidney function results in a contraindication for metformin use. Metformin is to be stopped if the subject's estimated glomerular filtration rate, calculated according to the Modification of Diet in Renal Disease formula, decreases during the study to a level where metformin is contraindicated according to its label (as appropriate for each participating country).

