5.1.3.5. Re-introduction of Insulin Lispro in the Albiglutide Treatment Group

Basal insulin plus once-weekly albiglutide may not provide adequate control of postprandial hyperglycemia in some subjects previously treated with basal-bolus insulin therapy. For subjects randomly assigned to treatment with albiglutide who continue to experience significant postprandial glucose excursions (i.e., >180 mg/dL [>10.0 mmol/L]), insulin lispro may be re-introduced after Week 8 (i.e., 4 weeks after discontinuation of insulin lispro and uptitration to albiglutide 50 mg). Re-introduction of insulin lispro will follow the standardized, stepwise approach as shown in [Figure 2](#).

Following the re-introduction of insulin lispro, subjects will remain in the study and continue to take insulin lispro in addition to randomly assigned once-weekly albiglutide and background insulin glargine. As determined by the investigator, subjects requiring re-introduction of insulin lispro may be seen more frequently by arranging unscheduled visits until their glycemic control has stabilized.

Figure 2 Re-introduction Algorithm for Insulin Lispro

HbA_{1c} = glycosylated hemoglobin. SMBG = self-monitored blood glucose.

Note: Figure modified with permissions (pending) from [Abrahamson 2012].

1. Post-breakfast (Prior to Lunch), post-lunch (Prior to Dinner), or post-dinner (i.e., Prior to Bedtime).
2. Mean of measurements from the last 3 available days (at least 2 of which are consecutive) in week before the next study visit/telephone contact. If measurements from 3 days (at least 2 of which are consecutive) are not available, the dose adjustment should be delayed until the next scheduled study visit/telephone contact; unless in the investigator's judgment, a dose adjustment is warranted. The subject should be retrained on the importance of SMBG measurements.
3. For insulin lispro dose titration, see Section 5.1.3.2, Table 4.

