The algorithm in Figure 2 for re-introduction of insulin lispro should apply in the majority of circumstances; however, as the intent of glycemia management in subjects with T2DM is to individualize treatment goals to achieve a target HbA_{1c} level as close to normal as possible without significant hypoglycemia or other adverse effects of treatment, the investigator should use his/her judgment in determining benefit:risk of further insulin dose adjustment and modification, accordingly. In the event a subject experiences significant evidence of hyperglycemia (e.g., symptoms of polyuria and polydipsia and laboratory evidence of hyperglycemia) and the investigator determines that further dose adjustment with insulin is not in the best interest of the subject and that the subject requires rescue with another antidiabetic medication, the subject should be discontinued from the study and the appropriate rescue therapy initiated. Additionally, subjects not achieving a predefined threshold for glycemic control (confirmed persistent FPG \geq 270 mg/dL [15.0 mmol/L]) at least 8 weeks after randomization may be considered

for study withdrawal based on the discretion of the investigator and the medical monitor (see Withdrawal Criteria in Section 4.5).

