6.7. Dose Titration and Insulin Lispro Re-introduction

The albiglutide dose in this study will start at 30 mg weekly and be titrated to 50 mg weekly at Week 4.

Both treatment arms will follow the same insulin glargine titration algorithm during the Standardization and Treatment Periods (see Table 3 of the Protocol).

Both treatment arms will follow the same insulin lispro titration algorithm during the standardization period. At randomization, the start of the treatment period, the insulin lispro titration algorithm will be individualized for each treatment arm (see Table 4 of the protocol).

Insulin lispro may be re-introduced after Week 8 for subjects in the albiglutide treatment group. The number of subjects for whom insulin lispro was re-introduced will be summarized. For these subjects, the re-introduced insulin lispro will be characterized in terms of the number of injections and the total dose over time. The dosing guidance for albiglutide, insulin lispro, insulin glargine, and metformin treatment can be found in Table 2 of the Protocol.

Individual dose titration information and insulin lispro re-introduction will be listed for the safety population.

For lispro re-introduction through Week 26, it will include lispro re-introduced up to Week 25 and not include lispro prescribed at Week 26. This is due to that the last albiglutide injection is given at Week 25 for subjects in albiglutide arm and at Week 26 lispro may be prescribed as per standard of care.

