8.1.3.4. Proportion of Subjects Achieving HbA_{1c} <6.5% at Week 26 and over Time

Proportion of subjects achieving HbA_{1c} target values of <6.5% at Week 26 and over time will be analyzed and summarized in a similar manner as specified in Section 8.1.3.3.

8.1.3.5. Incidence and Time to Meeting Prespecified Criteria for Severe, Persistent Hyperglycemia through Week 26

In this treat-to-target study design, subjects may be withdrawn if they have severe and persistent hyperglycemia. Meeting prespecified criteria for severe, persistent hyperglycemia at week 26 will be defined operationally as being withdrawn due to lack of efficacy as recorded on the Treatment Discontinuation and Study Conclusion eCRF pages. Proportion of subjects who meet prespecified criteria for severe, persistent hyperglycemia at Week 26 will be summarized and analyzed in a same manner as described in Section 8.1.2.2.

The time to meeting prespecified criteria for severe, persistent hyperglycemia through Week 26 will be calculated as the number of days between the date of first dose of randomized study medication and the date of meeting prespecified criteria, persistent hyperglycemia, plus 1. Subjects who do not meet the criteria will be censored at the date of the Week 26 visit or the date of the early termination visit if the subject terminated the study early. Kaplan-Meier estimates of the median time to meeting the criteria and 95% confidence interval for each treatment group will be presented. The treatment difference will be assessed using a log-rank test. The proportion of subjects meeting the criteria up to Week 26 (Day 182) based on Kaplan-Meier estimates will be displayed in the summary table. Kaplan-Meier curves of the times to meeting the criteria for each treatment group will be presented.

The analysis will be performed on FA population and all data will be listed.

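### SAP 8.1.2.1 and 8.1.3.5 give one criterion name two definitions that are not complements, and 8.1.2.1 has no rule for a lack-of-efficacy withdrawal with no lispro recorded up to Week 25

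*SAP*

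**What the plan says.** SAP 8.1.2.1 covers the key secondary endpoint on replacing prandial insulin. Subjects who do not meet the prespecified criteria for severe, persistent hyperglycemia are taken to be "those subjects treated with once-weekly albiglutide that are able to replace prandial insulin without lispro re-introduction through Week 26". A note closes the re-introduction window at Week 25. The proportion and its 95% confidence interval are reported for all albiglutide-arm subjects in the full analysis (FA) population and by subgroup. Early withdrawals are not mentioned.

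SAP 8.1.3.5 uses the same criterion name in both arms. Meeting the criteria "will be defined operationally as being withdrawn due to lack of efficacy", as recorded on the eCRF pages for treatment discontinuation and study conclusion. For the rest, "Subjects who do not meet the criteria will be censored at the date of the Week 26 visit", or at the early termination visit.

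The protocol does not settle which meaning applies. In Section 2 the objective refers to re-introduction of lispro, while the endpoint refers to stopping lispro at Week 4 and not meeting the criteria. Protocol 8.3.3.2 analyses re-introduction. No section sets out criteria under that name.

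Three protocol rules determine who lands where:
- Under 5.1.3.5, "insulin lispro may be re-introduced after Week 8", and "Following the re-introduction of insulin lispro, subjects will remain in the study and continue to take insulin lispro".
- The same section provides that, when further insulin is judged not to be in the subject's interest and another drug is needed, "the subject should be discontinued from the study and the appropriate rescue therapy initiated". Prior lispro re-introduction is not named as a condition.
- Under 5.7.1, lispro may be re-introduced by the same algorithm in the four weeks after an early withdrawal visit.

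**The concern.** One label should have one meaning, or the difference should be stated. Here a reader who sees the 8.1.2.1 proportion next to Table 2.101 would expect the two to add to 100% in the albiglutide arm. They need not.

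The more practical matter is the unscored subject. The key secondary objective asks how many patients can do without prandial insulin. A patient who left because glucose control failed, without lispro, is hard to call a success on that question. Yet 8.1.2.1 tests only for re-introduction, and this patient has none. The SAP does deal with withdrawals for other endpoints: 8.1.3.3 scores an HbA1c value missing for lack of efficacy or safety as not meeting target and shows this beside the observed data, and Table 2.43 repeats the hypoglycemia analysis without early withdrawals. The titles of Tables 2.31 to 2.34 show nothing comparable. Two programmers could score the same subject differently, and the more favorable scoring is the one that follows from the test as written.

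**Working it through.** **Inputs.** Albiglutide arm: 397 (SAP 2.3.2 and 11.12). Lack-of-efficacy withdrawals: no rate is given; SAP 11.6.3.2 does not expect a substantial number. The rates of 1%, 2% and 5% below are assumptions.

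**The plan's own figure.** With margin 0.3, SD 1.2, true difference 0, one-sided 0.025 and 90% power, n per arm = 2 × (1.2/0.3)² × (1.960 + 1.282)² ≈ 336.3, rounded up to 337. Allowing for 15% dropout, 337/0.85 = 396.5, rounded up to 397. The denominator reproduces and is not in dispute. There is no planning figure for this endpoint.

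**Cross-classification of the albiglutide arm**, for subjects who stopped lispro at Week 4:

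| Lispro re-introduced up to Week 25 | Withdrawn for lack of efficacy | 8.1.2.1 | 8.1.3.5 | Agree? |
|---|---|---|---|---|
| No | No | criteria not met (success) | not met | yes |
| Yes | Yes | not a success | met | yes |
| Yes | No | not a success | not met, censored | no |
| No | Yes | success by the only test given | met | no |

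Two of the four cells disagree, so the definitions are not complements. The third row arises by design, because subjects re-started on lispro stay in the study. It affects labelling and does not bias either figure. The fourth row affects the 8.1.2.1 proportion itself.

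**Size of the fourth row.** If k subjects fall there, the proportion is higher by k/397 than if they were non-successes.
- One subject: 1/397 = 0.25 points.
- 1%: k = 0.01 × 397 ≈ 4; 4/397 = 1.0 point.
- 2%: k = 0.02 × 397 ≈ 8; 8/397 = 2.0 points.
- 5%: k = 0.05 × 397 ≈ 20; 20/397 = 5.0 points.

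As an illustration, take an assumed 278 of 397 recorded successes (70.0%). Re-scoring 4 of them gives 274/397 = 69.0%; re-scoring 20 gives 258/397 = 65.0%.

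**Scale.** The 95% confidence interval half-width is 1.96 × √(p(1−p)/397): 4.9 points at p = 0.5 and 3.9 points at p = 0.8.

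**The case against.** The strongest reply is that the direction is not fixed. The operational definition speaks of being able to replace prandial insulin through Week 26, which can be read as requiring the subject to stay on treatment. That reading is possible, but the SAP does not state it, and Table 2.32 also groups subjects by re-introduction status alone.

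A reader might infer that every lack-of-efficacy withdrawal counts as a success. The documents do not support that. Protocol 5.7.1 lets lispro be re-introduced after an early withdrawal visit, and a subject given it before Week 25 could be a failure under 8.1.2.1. Nor does SAP 6.7 rule this out: "For lispro re-introduction through Week 26, it will include lispro re-introduced up to Week 25 and not include lispro prescribed at Week 26" excludes only Week 26 prescriptions and is silent on early withdrawals. The point therefore holds only where no lispro is recorded up to Week 25.

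A reader might also infer that withdrawals between Weeks 4 and 8 are a built-in source of false successes, since lispro cannot yet return. No section describes such a withdrawal. The fasting glucose option starts at least 8 weeks after randomization, and the rescue sentence follows the re-introduction algorithm and concerns further insulin adjustment.

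Other mitigating facts stand. SAP 8.1.2.1 limits its definition to this endpoint, follows Protocol 8.3.3.2, and has a table (2.31) titled by what it counts. Part of the difference is structural, because Protocol Table 2 marks re-introduction as not applicable in the control group. Table 2.101 caps the possible overstatement, and Tables 1.03 and 1.04 give the reasons for leaving. None of this supplies the missing scoring rule.

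**Conclusion.** The point holds as a minor one. The same criterion name carries two operational definitions that are not complements. By the only test in 8.1.2.1, a subject withdrawn for lack of efficacy with no lispro recorded up to Week 25 is a success. The effect favors albiglutide and is probably about 1 point or less, because few such withdrawals are expected; 1 to 5 points corresponds to an assumed 1% to 5% of 397. The rate is an assumption throughout.

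A reader might infer a wide numerical gap between the two results from the shared label. The documents give no re-introduction rate from which to size it, and it would reflect naming and not bias. A reader might also infer a threat to the trial's main claim. There is none: SAP 11.10 says a treatment comparison does not apply to this one-arm endpoint and leaves it out of the test sequence, so alpha, power and the primary conclusion are unaffected.

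**What to change.** 1. In SAP 8.1.2.1, count a success only if lispro was stopped at Week 4, was not re-introduced up to Week 25, and the subject was not withdrawn for lack of efficacy as recorded on the eCRF pages already used in 8.1.3.5. Keep such withdrawals in the FA denominator as non-successes. State whether lispro re-introduced after an early withdrawal visit counts as re-introduction.
2. Name the 8.1.2.1 endpoint by what it counts, as the Table 2.31 title already does. Reserve severe, persistent hyperglycemia for 8.1.3.5, and state that the two are not complements. There is no need to force one definition on both sections.

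Optional: add a row to Table 2.31 with all early withdrawals as non-successes, which would also cover safety and procedural withdrawals.

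The cost is SAP wording, one flag from data already collected and, if wanted, one table row. The downside is that the reported proportion may be slightly less favorable.
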